9.5.2.1.4 Reporting Adverse Events and Serious Adverse Events

At each visit, patients are to be queried regarding any AEs or SAEs that have occurred since the previous visit. Patients will be asked to volunteer information with a nonleading question such as, "How do you feel since your last visit?" Study center personnel will record all pertinent information in the patient's eCRF.

All AEs must be recorded on the appropriate AE reporting page of the patient's eCRF whether or not they are considered causally related to the IP.

For every AE, the Investigator must:

• Provide an assessment of the seriousness of the event (ie, is it an SAE?), as well as the severity and casual relationship

- Document all actions taken with regard to the IP
- Detail any other treatment measures taken for the AE
- Document the outcome of the AE

In addition, patients are to be reminded, as described in the ICF and in accordance with Section 9.5.2.1, to notify study center personnel of any AEs occurring during the 30-day poststudy period. Any AEs reported by the patient (or patient representative) during this period are to be recorded in original source documents. AEs are also to be recorded in the eCRF if at least one of the following conditions is met: 1) the event meets the criteria for an SAE (see Sections 9.5.2.1.3 and 9.5.2.1.4), and/or 2) the event is judged by the Investigator to be potentially causally related to IP.

Any AEs that are ongoing at the time of the final protocol-defined study visit will be followed until the condition returns to prestudy status, has resolved or stabilized, or can be explained as being unrelated to the IP. If a follow-up visit is deemed necessary for appropriate safety surveillance, it will take place within 30 days of the final protocol-defined study visit.

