10.1	Adverse Events	
1. The definitions of TEAE and SAE were revised to use the first dose of DB IP as the reference and remove the condition of study entry into RAP-MD-04 since the enrollment of subsequent study could not be fully confirmed by study data of RAP-MD-01
 
2. The incidence of common TEAEs by 5% criteria was removed
 
3. The term, on-therapy SAE is revised to be treatment emergent SAE (TESAE)

12.0	Interim Analyses	Texts were revised in accordance with the changes in protocol addendum amendment 2
13.0	Determination of	Texts were revised in accordance with the changes in

Section No.	Section Name	Description
	Sample Size	protocol addendum amendments 2 and 3
15.1	Visit Time Windows	
1. Two separate windows were created (one for baseline at Day 0 analyses and another for Baseline at Day 7 analyses).2. Naming convention for scheduled visit was revised by “Day x”3. Definition of Indices was revised for the scenarios when the scheduled dosing of study treatment did not occur
15.2	Derived Efficacy and Safety Variables	The list of derived efficacy and safety variables was removed since the derivation algorithms were stated in Sections 9, 9.3, and 10.5 for corresponding parameters.
15.6	Missing Date Information for Adverse Events	An additional rule was added to impute the missing AE date: if the patient did not receive any randomized dosing during the study, then the date of first dose of DB IP will be utilized for comparison and imputation
15.7	Missing Date Information for Prior or Concomitant Medications	An additional rule was added to impute the missing medication date: if the patient did not receive any randomized dosing during the study, then the date of first dose of DB IP will be utilized for comparison and imputation
15.9	Actual Treatment for Analysis	Section was removed since the safety analyses is changed to be based on the treatment randomized. The previously proposed algorithm to determine the treatment actually received when wrong kits of study treatments were dispensed is no longer applicable
18.0	Appendix II	
1. Section was revised with enhanced details for the statistical method, Pattern-Mixture Model2. The SAS codes were removed from SAP to a separate document for statistical programming

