10.1 ADVERSE EVENTS

AEs will be coded using the *Medical Dictionary for Regulatory Activities* and reported separated for placebo lead-in, randomized treatment, and safety follow-up periods.

[figure not shown]
An AE (classified by preferred term) will be considered a treatment-emergent adverse event (TEAE) if it was not present before the first dose of DB IP (i.e. the first IP during the placebo lead-in period) or was present before the date of the first dose of DB IP and increased in severity after the first dose of DB IP. An AE that becomes serious after the date of the first dose of DB IP will also be considered as TEAE. If more than 1 AE was reported before the first dose of DB IP and coded to the same preferred term, the AE with the greatest severity will be used for comparison with the AEs occurring during each study period analyzed. An AE that occurred more than 30 days after the date of the last dose of DB IP (including the randomized IP) will not be considered as a TEAE.

[figure not shown]
The number and percentage of patients reporting TEAEs and TEAEs leading to study discontinuation in each treatment group will be tabulated by system organ class and preferred term and further categorized by severity and causal relationship to the IP. If more than 1 AE is coded to the same preferred term for the same patient, the patient will be counted only once for that preferred term using the greatest severity and strictest causality for the summarization by severity and causal relationship.

The incidence of common ($\geq 2\%$ of patients in any treatment group) TEAEs will be summarized by preferred term and treatment group and sorted by decreasing frequency for the test treatment.

A serious adverse event (SAE) that occurred between the date of the first dose of DB IP and 30 days after the date of the last dose of DB IP, inclusive, will be considered a treatment-emergent SAE (TESAE). The number and percentage of patients who have TESAEs will be summarized by preferred term and treatment group.

[figure not shown]
Listings will be presented for patients with SAEs, patients with AEs leading to discontinuation, and patients who die (if any). All patients with SAEs, including SAEs reported during the screening period and the safety follow-up period, and patients discontinuing because of AEs occurring before the start of randomized IP will be included in these listings.

[figure not shown]

[figure not shown]

[figure not shown]

RESTRICTED

RESTRICTED

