15.6 MISSING DATE INFORMATION FOR ADVERSE EVENTS

The following imputation rules only apply to cases in which the start date for an AE is incomplete (ie, partly missing). If the patient did not receive any randomized dosing during the study, then the date of first dose of DB IP will be utilized for the purpose of imputation.

Missing month and day

- If the year of the incomplete start date is the same as the year of the first dose of randomized IP, the month and day of the first dose of randomized IP will be assigned to the missing fields.
- If the year of the incomplete start date is before the year of the first dose of randomized IP, *31 Dec* will be assigned to the missing fields.
- If the year of the incomplete start date is after the year of the first dose of randomized IP, *01 Jan* will be assigned to the missing fields.

Missing month only

- If only the month is missing, the day will be treated as missing and both the month and the day will be replaced according to the above procedure.

Missing day only

- If the month and year of the incomplete start date are the same as the month and year of the first dose of randomized IP, the day of the first dose of randomized IP will be assigned to the missing day.
- If either the year of the incomplete start date is before the year of the date of the first dose of randomized IP or if both years are the same but the month of the incomplete start date is before the month of the date of the first dose of randomized IP, the last day of the month will be assigned to the missing day.
- If either the year of the incomplete start date is after the year of the date of the first dose of randomized IP or if both years are the same but the month of the incomplete start date is after the month of the date of the first dose of randomized IP, the first day of the month will be assigned to the missing day.

If the stop date is complete and the imputed start date as above is after the stop date, the start date will be imputed by the stop date.

If the start date is completely missing and the stop date is complete, the following algorithm will be used to impute the start date:

- If the stop date is after the date of the first dose of randomized IP, the date of the first dose of randomized IP will be assigned to the missing start date.
- If the stop date is before the date of the first dose of randomized IP, the stop date will be assigned to the missing start date.

15.7

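### SAP 15.6 dates partly known AE onsets to the first randomized dose although SAP 10.1 starts treatment emergence at the lead-in dose, so ongoing screening or lead-in events can be dated to Day 7

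*SAP*

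**What the plan says.** **Imputation (SAP 15.6).** The reference is the first randomized dose.
- Month and day missing, year matching: "the month and day of the first dose of randomized IP will be assigned to the missing fields".
- Day missing, month and year matching: "the day of the first dose of randomized IP will be assigned to the missing day".
- Start wholly missing, complete stop date after that dose: "the date of the first dose of randomized IP will be assigned to the missing start date".
- Known month or year earlier than the reference: last day of that month or year. Later: first day.
- Exception: "If the patient did not receive any randomized dosing during the study, then the date of first dose of DB IP will be utilized" as the reference. Such patients are outside the Safety Population of SAP 5.2. The entry for 15.6 in the change history (SAP 2.0) reports this exception and nothing else: "An additional rule was added to impute the missing AE date: if the patient did not receive any randomized dosing during the study".
- Guard: an imputed start later than a complete stop date is pulled back to the stop date. No rule looks at the visit at which the event was recorded.

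**Definition (SAP 10.1).** An AE is treatment-emergent if it was not present before the first double-blind dose, the placebo given at the start of the lead-in, or if it worsened afterwards. AEs are "reported separated for placebo lead-in, randomized treatment, and safety follow-up periods". The change history for this section confirms the move: "The definitions of TEAE and SAE were revised to use the first dose of DB IP as the reference".

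**Neighbouring rules (SAP 15.4 and 15.5).** Missing severity and missing causality are handled relative to the first double-blind dose.

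**Collection (Protocol 9.5.2.1 and 9.5.2.1.4).** AEs are collected from consent, and at each visit "patients are to be queried regarding any AEs or SAEs that have occurred since the previous visit".

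**The concern.** The definition and the imputation use reference dates a week apart. The amendment moved the TEAE definition to the lead-in dose, but SAP 15.6 gained only the exception for patients with no randomized dose.

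Two wrong results follow for patients who did receive one. A lead-in event that is ongoing, lacks a complete stop date, or stops on or after Day 7 can be given a start later than the visit that recorded it, and be counted in the randomized period. A screening event of the same kind can in addition become treatment-emergent although it began before any dose. The lead-in table loses events, and the randomized-period table gains events that randomized treatment cannot have caused.

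**Working it through.** The plan gives no figure on this point, so there is none to reproduce.

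**Inputs from the documents**
- Screening up to 14 days and a 1-week lead-in (SAP 3.0): Days −14 to −1 and Days 0 to 6.
- First randomized dose nominally 7 days after the lead-in dose (SAP Tables 15.1–1 and 15.1–2).
- Visits on the dosing day and 1, 4 and 7 days later (Protocol 9.1.2): Visit 2 is Day 0, Visit 3 Day 1, Visit 5 Day 7.

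**Assumptions, not in the documents**
- Only the day of onset is missing, and the event is ongoing, so the stop-date guard does not act.
- True onset is spread evenly within each period and over the calendar, and the first randomized dose is exactly on Day 7.

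**Step 1: worked example.** Lead-in dose 8 March, Visit 3 on 9 March, first randomized dose 15 March. Each AE start is known only as March.
- Recorded at Visit 3, ongoing: start set to 15 March. 15 − 9 = 6 days after the site recorded it.
- True onset 10 March (lead-in), ongoing: set to 15 March, so it moves to the randomized period.
- True onset 2 March (screening), ongoing: set to 15 March, so a pre-dose event appears as a randomized-period TEAE.
- True onset 10 March, complete stop date 12 March: pulled back to 12 March and stays in the lead-in. The guard works here.

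**Step 2: share dated to Day 7.** For onset g days before the first randomized dose, with a mean month of 365/12 = 30.4 days, P(same month) ≈ 1 − g/30.4.
- Lead-in: g = 1 to 7, mean 4. 1 − 4/30.4 = 0.87.
- Screening: g = 8 to 21, mean 14.5. 1 − 14.5/30.4 = 0.52.

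**Step 3: full enumeration.** The rule was applied to every lead-in date in a 365-day year and every onset day, first with the current reference and then with the first double-blind dose substituted throughout.

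| True onset | Reference | Dated pre-dose | Dated in lead-in | Dated Day 7 or later |
|---|---|---|---|---|
| Screening, Days −14 to −1 | Randomized dose (current) | 24.7% | 23.0% | 52.3% |
| Screening | Double-blind dose | 24.7% | 75.3% | 0% |
| Lead-in, Days 0 to 6 | Randomized dose (current) | 0% | 13.2% | 86.8% |
| Lead-in | Double-blind dose | 0% | 100% | 0% |
| Randomized, Days 7 to 20 | Randomized dose (current) | 0% | 0% | 100% |
| Randomized | Double-blind dose | 0% | 75.3% | 24.7% |

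The enumeration agrees with Step 2. Under the current rule 52.3% + 23.0% = 75.3% of these screening onsets are dated on or after the first double-blind dose; the 23.0% arises from the end-of-month rule. Simply substituting the double-blind dose leaves that 75.3% unchanged and moves 75.3% of true randomized-period onsets back into the lead-in.

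**The case against.** **The rule may be deliberately cautious.** It keeps ambiguous events in the randomized period and does not credit possible drug effects to lead-in placebo. This stands for events first reported after the first randomized dose, and Step 3 shows what a plain substitution would cost. It does not stand for events already on record before that dose, where a later start date is simply wrong.

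**Few events are affected.** Patients are asked about AEs at closely spaced visits, and incomplete entries are queried (Protocol 9.6.2). This stands. It also removes most of the weight from the year-only case: 1 − 4/365 = 0.99 and 1 − 14.5/365 = 0.96 might suggest that nearly all such events move, but a year-only start for an event elicited within days is implausible.

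**Period allocation is not spelled out.** SAP 10.1 gives no rule for assigning an event to a period, and the table specifications are in a separate document. An event recorded before dosing is also known to have been present then. This stands as a caveat: the misallocation follows if the tables are programmed from the imputed date, the natural reading of a section whose purpose is to supply one.

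**Readings the documents do not support.** A reader might infer that the error compounds generally with SAP 15.4 and 15.5. It does not: both use the first double-blind dose, so a lead-in AE lacking severity or causality becomes severe or related whether dated Day 1 or Day 7. Only a screening AE that lacks both a full start date and severity or causality is affected. A reader might also infer that one arm is favoured. The rule is identical in both arms and safety is summarized descriptively. Similar additions to both arms leave the expected risk difference about unchanged and pull a rate ratio toward 1.

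**Conclusion.** The mismatch between SAP 15.6 and SAP 10.1 is in the current text, and it gives a wrong date whenever an AE already recorded before the first randomized dose is imputed to that dose. A lead-in event is treatment-emergent either way and only its period changes; a screening event can also gain TEAE status.

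The 87% and 52% are conditional on a missing day, no earlier complete stop date, evenly spread onset and a first randomized dose on Day 7. They are not shares of all AEs. The frequency of partial dates is not given and is probably small. This is a minor correction to the period-specific safety tables; nothing in it bears on the efficacy analyses.

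**What to change.** Amend SAP 15.6:

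- (a) The imputed start date may not be later than the date of the visit at which the AE was first recorded.
- (b) An AE first recorded before the first double-blind dose, including pre-dose at Visit 2, is imputed to a date before that dose and treated as pre-dose. Without this clause the cap for an AE recorded at Visit 2 would be Day 0 itself, and the event could still count as treatment-emergent.
- (c) For an AE first recorded after the first double-blind dose and up to the pre-dose part of Visit 5, the partial date is compared with the first double-blind dose.
- (d) The current rule stays for AEs first recorded after the first randomized dose.

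The cost is a short SAP paragraph and a programming check, and it needs the recording visit or date from EDC. Late entry loosens the cap, at worst back to the current rule. A lead-in event first reported only after the randomized dose would still be dated to Day 7.

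The medication rules should be reviewed at the same time: SAP 7.0 separates prior from concomitant use at the first double-blind dose, while SAP 15.7 imputes start dates against the first randomized dose.

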9.7.6.1 Adverse Events

All AEs will be coded by system organ class and preferred term using the *Medical Dictionary for Regulatory Activities*.

An AE (classified by preferred term) will be considered a treatment-emergent adverse event (TEAE) if it was not present before the first dose of IP or was present before the date of the first dose of IP and increased in severity after the first dose of IP. An AE that becomes serious after the date of first dose of IP will also be considered as a TEAE. If more than 1 AE is reported before the first dose of IP and coded to the same preferred term, the AE with the greatest severity will be used for comparison with the AEs occurring during the double-blind treatment period that were also coded to that preferred term. An AE that occurs more than 30 days after the date of the last dose of IP will not be considered as a TEAE.

The number and percentage of patients reporting TEAEs in each treatment group will be tabulated by system organ class and preferred term and further categorized by severity and causal relationship to the IP. If more than 1 AE is coded to the same preferred term for the same patient, the patient will be counted only once for that preferred term using the greatest severity and strictest causality for the summarization by severity and causal relationship.

A serious adverse event (SAE) that occurred between the date of the first dose of IP and 30 days after the date of the last dose of IP, inclusive, will be considered a treatment-emergent SAE (TESAE). The number and percentage of patients who have on-therapy TESAEs will be summarized by preferred term and treatment group. In addition, the incidence of on-therapy SAEs that lead to death will be summarized separately by preferred term for each treatment group.

Overall summaries of AEs will be provided on a per-patient basis for categories of all TEAEs, treatment-related TEAEs, TESAEs, and TEAEs leading to study discontinuation.

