5.2 SAFETY POPULATION

The Safety Population will consist of all patients who were randomized and received at least 1 dose of IP during the randomized treatment period.

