8.0 EXTENT OF EXPOSURE AND TREATMENT COMPLIANCE

8.1 EXTENT OF EXPOSURE OF STUDY TREATMENT

The number and percentage of patients who received 1 or 2 randomized IV doses will be summarized by treatment group for the Safety Population. IV administration notes including site reaction at placement of IV, reaction to adhesive, infusion interruption, failure of administration device, increase in suicidality based on clinical evaluation, and perceptual disturbance based on mental status assessment are collected. For each item, the number and percentage of patients who had a 'yes' response will be summarized by treatment group and visit for the Safety Population.

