If any, the centers with only placebo responder patients will be ordered from largest to the smallest by the number of patients. The smallest pooled center (based on placebo non-responder as defined in the previous paragraph) will be combined with largest center with only placebo responder patients; the second smallest pooled center (based on placebo non-responder as defined in the previous paragraph) will be combined with the second largest center with only placebo responder patients; the remaining centers with only placebo responder patients will be combined similarly. Centers with same number of patients will be further ordered by the center code.

The final pooled pseudo-centers will be used for all efficacy analyses when the model is adjusted for study center.

The efficacy analyses of MADRS assessments will be based on the rater-administered MADRS. The efficacy analyses using the mITT population will be performed based on the treatment to which the patient is randomized regardless of the actual treatment received. If a patient is randomized based on an incorrect stratum, then this patient will be analyzed according to the stratum to which the patient should have been assigned per the electronic data capture system, instead of the stratum per the randomization system of IWRS.

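### Safety is analysed by treatment randomized with no treatment-received tables, so adverse events after a wrong kit would be counted under the randomized arm

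*SAP*

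**What the plan says.** The SAP's History of Changes has an entry for Section 15.9, Actual Treatment for Analysis: "Section was removed since the safety analyses is changed to be based on the treatment randomized". It continues: "The previously proposed algorithm to determine the treatment actually received when wrong kits of study treatments were dispensed is no longer applicable". The entry describes the basis adopted in the current amendment, so it is the rule in force.

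The visible body has no treatment-received rule for safety:

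- SAP 5.2 settles who is in the Safety Population, not which arm a patient is counted in: "The Safety Population will consist of all patients who were randomized and received at least 1 dose of IP during the randomized treatment period".
- SAP 10.1 works by treatment group and does not define the term by assignment or receipt. For serious events: "The number and percentage of patients who have TESAEs will be summarized by preferred term and treatment group". The common-event table, with its 2% cut-off, uses the same label: "of patients in any treatment group) TEAEs will be summarized by preferred term and treatment group".
- SAP 9.0 does address assigned versus actual treatment, but only for efficacy in the mITT Population, where analysis is "based on the treatment to which the patient is randomized regardless of the actual treatment received".
- Section 15, as far as it is shown, has no treatment-received algorithm.

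The open protocol is silent too. Its Section 9.7.6.1 says: "The number and percentage of patients reporting TEAEs in each treatment group will be tabulated by system organ class and preferred term", and its Safety Population (9.7.1.2) is defined by dosing alone.

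**The concern.** For efficacy, analysis by assigned arm preserves the randomized comparison. For safety, a patient who received the other arm's product carries that product's risk into the wrong column. If rapastinel raises the risk of an event, mixing the arms shrinks the observed difference on average, which is the less cautious direction for a safety table.

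Kits are obtained through the IWRS at each dosing visit (Protocol 9.4.5 and 9.4.7.2), and a patient may have one or two randomized doses (SAP 8.1: "The number and percentage of patients who received 1 or 2 randomized IV doses will be summarized by treatment group for the Safety Population"). A patient could therefore be wrong at one dose or at both. With one right and one wrong kit, only events after the wrong dose are in question. The practical stake is a rare serious event, where one patient decides what the table shows.

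**Working it through.** The plan gives no figure for this issue, so there is none to reproduce. The check is one of scale.

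**Inputs.** N = 230 per arm (Protocol 9.7.9, SAP 13.0). The common-event cut-off is 2% in any treatment group (SAP 10.1). The documents give neither a wrong-kit count nor event rates. The number m of switched patients in each arm and the true event risks p1 (rapastinel) and p0 (placebo) are therefore assumed.

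**1. Average dilution.** Let f be the share of the excess risk that moves with the wrong dose or doses.

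- Rapastinel column: p1 − (m/N)·f·(p1 − p0)
- Placebo column: p0 + (m/N)·f·(p1 − p0)
- Difference: (p1 − p0)·(1 − 2mf/N)

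| m per arm | both doses wrong (f = 1) | an assumed 8.0-point difference becomes (f = 1) | one of two doses wrong (f = 0.5, assumed) |
|---|---|---|---|
| 1 | 1 − 2/230 = 99.1% | 7.93 | 99.6% |
| 2 | 1 − 4/230 = 98.3% | 7.86 | 99.1% |
| 5 | 1 − 10/230 = 95.7% | 7.65 | 97.8% |

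**2. A single serious event.** Suppose one patient is switched and has the only serious event in the trial.

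- Randomized to placebo, received rapastinel: the table shows 0/230 on rapastinel and 1/230 on placebo (−0.43 points). By treatment received it would be 1/231 and 0/229 (+0.43 points). Rapastinel risk is understated.
- Randomized to rapastinel, received placebo: the table shows 1/230 and 0/230 (+0.43 points). By treatment received it would be 0/229 and 1/231 (−0.43 points). Rapastinel risk is overstated.

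**3. The 2% cut-off.** 0.02 × 230 = 4.6, so a term needs 5 patients in one arm (5/230 = 2.17%; 4/230 = 1.74%). Take as-treated counts X ~ Bin(230, p1) and Y ~ Bin(230, p0), and swap m patients each way. The numbers of cases moved, A and B, are then hypergeometric. A term is lost if max(X, Y) ≥ 5 but max(X − A + B, Y + A − B) < 5, and gained in the reverse case. Exact sums for m = 1, 2, 5:

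| p1, p0 (assumed) | chance a given term is lost | chance a given term is gained |
|---|---|---|
| 2%, 0.5% | 0.37%, 0.74%, 1.81% | 0.11%, 0.21%, 0.49% |
| 2%, 1% | 0.34%, 0.67%, 1.61% | 0.22%, 0.44%, 1.05% |
| 2%, 2% | 0.24%, 0.48%, 1.13% | 0.24%, 0.48%, 1.13% |

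At 2% versus 1% the net loss is about 0.11%, 0.23% and 0.56%. With equal rates it is zero. A term lost from the common-event table still appears in the table by system organ class and preferred term.

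**The case against.** The strongest reply is that the sponsor made this choice openly and stated its consequence. No visible text promises an as-treated safety analysis, so no commitment is broken. That stands.

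The trigger is also hypothetical. The IWRS names the kit at each dosing visit and confirms each transaction (Protocol 9.4.5), and the syringe carries the kit number and the patient number (Protocol 9.4.3). Five fully switched patients per arm would mean ten patients wrong at both doses, which is an upper illustration rather than an expectation.

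Rare events are also normally read case by case. SAP 10.1 lists patients with serious events, discontinuations due to adverse events, and deaths. SAP 6.1 tabulates and lists significant deviations, Protocol 9.10 counts dosing among possible deviations, and a DSMB reviews safety data (Protocol 9.8). These safeguards are real, but none changes the incidence tables. A wrong kit also reaches the deviation listing only if it is classed as significant, under criteria in a separate document.

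Three stronger readings are tempting. A reader might infer from the change log's mention of wrong kits that some were dispensed; it describes when the withdrawn algorithm applied and reports no event. A reader might infer that the SAP contradicts the protocol; the open protocol has no treatment-received rule to contradict. A reader might infer that the rule hides rapastinel harm; the average effect is dilution, but a single event or a term near the cut-off can move either way.

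**Conclusion.** The point holds as a low-severity, conditional gap. Under the stated rule, events after a wrong kit are counted under the randomized arm, and no planned table visible in the SAP shows them by treatment received.

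For common events the effect is small: less than 1% of the risk difference for each fully switched patient per arm. At the 2% cut-off it is negligible and runs both ways. It matters mainly for a rare serious event, which one switched patient can place in the wrong column.

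The sizes rest on the planned 230 per arm and on assumed values of m, f, p1 and p0. If no wrong kit was dispensed, nothing changes. Parts of SAP Section 10, the separate table specifications and the Restricted Access Addendum named in SAP 3.0 were not available, so a rule there cannot be strictly excluded, although the change log says the algorithm was removed.

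**What to change.** Keep the as-randomized safety tables, and keep efficacy as randomized. Before unblinding, add to SAP 10.1 that if any wrong kit was dispensed in the randomized period:

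- TEAE and TESAE tables by treatment received will also be produced, with a stated rule for mixed doses (for example, counted as rapastinel if any rapastinel dose was received).
- Each affected patient will be listed, with the adverse events and the dose they followed.

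The same edit can state the as-randomized label for the main safety tables, which the visible text now gives only in the change log.

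The cost is a short text change and, only if a wrong kit occurred, modest programming. Kit numbers would have to be reconciled from IWRS notifications and source records (Protocol 9.4.3 and 9.4.5); no visible text shows them in the analysis database. No single rule classifies mixed-dose patients perfectly. Under the example rule, a rapastinel-randomized patient with one placebo kit keeps the rapastinel label, so the listing has to carry the detail.
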